- The BPRS+, which is one of the oldest, most widely used rating scales to measure psychotic symptoms and will be used by the study staff to measure psychiatric symptoms such as depression, anxiety, hallucinations and unusual behavior.
- The 5D-ASC, which will be used to assess the quality of acute psychological effects of the PCN-101 infusion.
- The C-SSRS, which will be used to assess the emergence of suicidal ideation. This instrument has been used frequently in clinical studies, and it is a standard measure for suicidal ideation assessment; its use is in accordance with US Food and Drug Administration guidance.

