8.2.10 Suicidal Risk Monitoring

PCN-101 is being investigated as an antidepressant/central nervous system-active study treatment. Although there has been some concern that these types of treatments may be associated with an increased risk of suicidal ideation or behavior when given to some subjects with MDD, other studies have indicated that ketamine may be associated with a decrease in suicidal ideation or behavior. Therefore, the Sponsor considers it important to monitor suicidal ideation and behavior and treatment-emergent suicidal ideation and behavior during the study.

The definitions of behavioral suicidal events used in this scale are based on those used in the Columbia-Suicide History Form. Questions are asked on suicidal behavior, suicidal ideation, and intensity of ideation. At screening (Visit 1), questions will be in relation to lifetime experiences.

Questioning at all subsequent visits (see [Section 1.3](#), Schedule of Activities) will be in relation to the last assessment (since last visit). The adult C-SSRS will be used for all subjects.

The C-SSRS will be administered to subjects at screening, at baseline, and prior to discharge from the clinic 24 hours after the infusion of study treatment. The C-SSRS will be administered to subjects at follow-up Visit 3 (Day 8) and Visit 4 (Day 15). Note: the C-SSRS may be evaluated by either efficacy or safety rater.

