For the C-SSRS: suicidal ideation and behavior scores at each assessment time as well as the incidence rate of TEAEs will be summarized using frequency counts and percentages by treatment group.

For the CADSS, BPRS+, 5D-ASC, and MOAA/S: Descriptive statistics of scores and their changes from baseline will be summarized at each assessment time by treatment group.

Pregnancy test and urine drug and alcohol screen will be presented in by-subject listings.

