2. TEAEs related to study drug (possibly, probably, definitely related or unknown)
3. Treatment-emergent SAEs
4. Treatment-emergent SAEs related to study drug (possibly, probably, definitely related or unknown)
5. Severe TEAEs

6. Severe TEAEs related to study drug (possibly, probably, definitely related or unknown)
7. TEAEs resulting in the permanent discontinuation of study treatment
8. TEAEs by maximum severity grade

The following AE listings (including both TEAEs and non-TEAEs) will be produced. AEs recorded at any time of the study (ie, not necessarily TEAEs only) will be included.

9. All AEs
10. All SAEs
11. Severe SAEs
12. AEs leading to discontinuation of study treatment
13. AEs leading to death

C. C-SSRS

The C-SSRS is a questionnaire used for suicide assessment developed by multiple institutions, including Columbia University. The scale is evidence-supported and is part of a national and international public health initiative involving the assessment of suicidality.

The number of subjects who reported “Yes” to each of the questions relating to suicidal ideation and suicidal behavior at any post-baseline timepoint will be summarized by treatment group.

All C-SSRS assessments details will be listed.

D. Clinical Laboratory Results

Laboratory values will be presented in tables and data listings using System International (SI) units.

For chemistry and hematology parameters, summaries of actual values and changes from baseline will be presented by treatment group for each scheduled assessment timepoint, beginning with the Baseline visit. For this analysis, any lab collection performed on unscheduled analysis visits will not be summarized, with the exception of the inclusion of unscheduled pre-dose assessments used in the classification of baseline, as described in [Section V.B Definition of Baseline](#).

For chemistry and hematology parameters, shift tables summarizing the number and percentages of patients who were normal at baseline, but who became abnormal subsequently, will also be displayed. For this analysis, any lab collection performed on unscheduled analysis visits will be included for analysis.

All laboratory data (including and not limited to chemistry, hematology, urinalysis, serology, pregnancy, urine alcohol, SARS-CoV-2) will be listed, including normal ranges and fasting status, if applicable.

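### The SAP's C-SSRS summary omits the by-visit table planned in the protocol and makes no reference to baseline, so for ideation Items 1-3 it cannot separate new from persisting ideation

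*SAP*

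**What the plan says.** SAP VIII.C counts, separately for each ideation and behavior question, the subjects whose answer was Yes "at any post-baseline timepoint will be summarized by treatment group". The only other output is a listing: "All C-SSRS assessments details will be listed".

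The protocol sets a wider purpose. Section 4.2 describes the C-SSRS as a scale "which will be used to assess the emergence of suicidal ideation". Section 8.2.10 states that "the Sponsor considers it important to monitor suicidal ideation and behavior and treatment-emergent suicidal ideation and behavior during the study". Section 9.4.3 plans that "suicidal ideation and behavior scores at each assessment time as well as the incidence rate of TEAEs will be summarized", as counts and percentages by arm.

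Pre-dose data exist. Section 8.2.10 says: "The C-SSRS will be administered to subjects at screening, at baseline, and prior to discharge from the clinic". It adds: "At screening (Visit 1), questions will be in relation to lifetime experiences". Every later C-SSRS asks about the time since the previous assessment. The post-baseline assessments are at 24 hours, Day 8 and Day 15.

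Exclusion 10 (Protocol 5.2) removes subjects with Item 4 or Item 5 ideation in the month before screening and those with suicidal behavior in the year before screening. It sets no limit on ideation below Item 4.

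**The concern.** Subjects with recurrent major depression and a HAM-D total above 20 can enter the trial with ideation at Items 1-3. If such a subject still reports it at 24 hours, Day 8 or Day 15, the SAP table counts that subject exactly as it counts one whose ideation appeared after the infusion. For those items, the table alone does not tell a reader how many cases in each arm are new.

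This matters because Protocol 8.2.10 itself raises both directions of effect: possible worsening with antidepressant-type treatments and a possible decrease with ketamine. If both occurred in one arm, they would partly offset each other in a count of any Yes. With 31 subjects per arm, chance imbalance in baseline ideation is also plausible, and a table without a baseline column would not reveal it.

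**Working it through.** The documents give no C-SSRS rate, threshold or planned comparison, so there is no figure to reproduce. The check is a comparison of texts, followed by an illustration.

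**Step 1: protocol against SAP.**

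| Element | Protocol | SAP VIII.C |
|---|---|---|
| Summary at each assessment time | Planned (9.4.3) | Absent |
| Emergence of ideation | Purpose of the scale (4.2); monitoring aim (8.2.10) | No new-or-worsened category |
| Baseline values | Collected at screening and Day -1 (8.2.10) | Listed, not tabulated |
| Any Yes after baseline, per question | Not specified | Planned |

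**Step 2: the C-SSRS against the SAP's other safety data.** TEAEs must be new or worsened after the start of infusion (VIII.B). Laboratory data have shift tables from normal at baseline (VIII.D). Vital signs and QTcF have change-from-baseline criteria (VIII.E, VIII.G). MOAA/S, CADSS and BPRS+ have change scores (VIII.I). The C-SSRS has a Day -1 assessment but no comparable output.

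**Step 3: which items are exposed.** Exclusion 10 screens out Items 4-5 and behavior, and later questions ask only about the time since the last assessment, so lifetime history does not carry forward. A post-baseline Yes on those questions is therefore likely to be new. It is not certain to be, because the exclusion window ends at the start of screening. Items 1-3 have no such protection.

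**Step 4: illustration for one question in Items 1-3.** All three rates are assumptions:
- b = share of subjects answering Yes at baseline
- s = share of those who still answer Yes after dosing
- e = share of the others who newly answer Yes

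Expected share with any post-baseline Yes = b·s + (1 − b)·e.

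Take e = 5% on placebo and 15% on active, a true ratio of 3.0 among subjects without the symptom at baseline. Take s = 80% on placebo.

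| b | Placebo | Active, s = 80% | Ratio | Active, s = 40% | Ratio |
|---|---|---|---|---|---|
| 0 | 5% | 15% | 3.00 | 15% | 3.00 |
| 20% | 20% | 28% | 1.40 | 20% | 1.00 |
| 40% | 35% | 41% | 1.17 | 25% | 0.71 |
| 60% | 50% | 54% | 1.08 | 30% | 0.60 |

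Worked row, b = 40%: placebo 0.40 × 0.80 + 0.60 × 0.05 = 0.35, or 10.9 of 31. Active with s = 40%: 0.40 × 0.40 + 0.60 × 0.15 = 0.25, or 7.8 of 31. Subjects at risk of a new Yes: 31 × 0.60 = 18.6 per arm. Expected new cases: 18.6 × 0.05 = 0.9 on placebo and 18.6 × 0.15 = 2.8 on active. The planned count would then be lower on active although new ideation is three times as frequent there. A count restricted to subjects without the symptom at baseline has an expected ratio of 3.0 in every row.

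**The case against.** Several points on the other side are sound.

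- **The table is not one pooled count.** Each question is counted separately, so a subject who moves from Item 2 to Item 4 appears under Item 4, and new behavior appears under behavior. A reader might infer that the plan is blind to all treatment-emergent suicidality. The item-level counts and Exclusion 10 do not support that reading for the most serious signals.
- **Improvement is not hidden.** A reader might infer that a fall in ideation would be invisible. The arms are randomized and the table is by arm, so ideation that resolves and stays resolved lowers that arm's count. Reducing ideation is also not a study objective; the C-SSRS is a safety measure.
- **The data are not lost.** Baseline C-SSRS is collected and every assessment is listed, so emergence can be worked out subject by subject among 93. The listing does not, however, prespecify a baseline, a definition of worsening or a comparison by arm.
- **Suicidality reported as an adverse event reaches the TEAE tables.** That route depends on event reporting rather than on the scale, and Protocol Appendix 4 excludes expected symptoms of the studied disease unless they are more severe than expected.
- **The protocol promises no shift table.** This is correct. Section 4.2 supports some reference to baseline but no particular format. The by-visit summary is different: Section 9.4.3 states it.

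**Conclusion.** Two things stand. First, SAP VIII.C omits the summary by assessment time that Protocol 9.4.3 states, and VIII.C gives no reason. Second, no planned C-SSRS table refers to baseline, so for Items 1-3 the summary cannot distinguish new ideation from persisting ideation. For Items 4-5 and behavior the weakness is small, on the assumption that few subjects develop these between the start of screening and dosing.

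The size cannot be stated from the documents. The illustration shows that masking or reversal is possible under assumed rates; it does not show that either is likely. If nobody reported the symptom at baseline, the planned count and a baseline-referenced count would agree.

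This is a modest reporting gap in a descriptive Phase 2a safety analysis and leaves the efficacy analysis untouched. It still deserves correction: the protocol makes emergence the purpose of the scale, there is no data monitoring committee (Protocol 9.6), and choices about baseline and worsening are best fixed before unblinding.

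**What to change.** Amend SAP VIII.C in three ways:

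1. Restore the summary of ideation and behavior by assessment time and arm, as in Protocol 9.4.3, and include the baseline visit. This shows baseline balance and change at arm level, but not emergence within subjects.
2. State which pre-dose assessment and recall window is the C-SSRS baseline. The general rule in SAP V.B, the last evaluable value before dosing, would point to Day -1. That assessment covers only the time since screening: from 1 day (Day -2 to Day -1) to 14 days (Day -15 to Day -1). Screening uses lifetime recall. The section should say which applies and why.
3. Add a table of worst post-baseline against baseline ideation category, with counts of new or worsened ideation and of new behavior by arm, each with its denominator.

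The cost is one or two extra descriptive tables from data already collected. No new assessment is needed, and SAP I.B allows changes until database lock.

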- Evidence of 2nd and 3rd degree atrioventricular block, complete left bundle branch block (LBBB), or complete right bundle branch block (RBBB).
- Features of new ischaemia.
- Arrhythmia (except premature atrial contractions [PACs] and premature ventricular contractions [PVCs]).
- Has a history of risk factors including hypokalemia or a family history of Long QT Syndrome.

8. Has known history of, or positive serology for, human immunodeficiency virus (HIV); has a positive hepatitis B surface antigen, and/or confirmed current hepatitis C infection (positive hepatitis C virus [HCV] antibody confirmed with reflex HCV ribonucleic acid [RNA] test). Subjects with a history of hepatitis B vaccination without a history of hepatitis B are allowed to enroll.

9. Has a history of malignancy within the 5 years prior to screening (exceptions are squamous and basal cell carcinomas of the skin and carcinoma in situ of the cervix, or a malignancy that in the opinion of the Investigator, with concurrence with the Sponsor's Medical Monitor, is considered to have minimal risk of recurrence).

10. Has homicidal ideation/intent per the Investigator's clinical judgment; or has suicidal ideation with some intent to act within 1 month prior to the start of screening per the Investigator's clinical judgment or based on the C-SSRS, corresponding to a response of "Yes" on Item 4 (active suicidal ideation with some intent to act, without specific plan) or Item 5 (active suicidal ideation with specific plan and intent); or a history of suicidal behavior within the past year prior to the start of the screening/prospective observational phase.

11. Has had major surgery (eg, requiring general or local anesthesia) within the 4 weeks before screening, or will not have fully recovered from surgery or planned surgery during the time the subject is expected to participate in the study.

12. Has moderately impaired hepatic function at screening, defined as serum alanine aminotransferase (ALT) or aspartate aminotransferase (AST) > 2 × upper limit of normal (ULN) or total bilirubin (TBL) > 2 × ULN.

13. Has received any disallowed therapies as follows (see [Section 6.5](#) for further details):

- a. Receipt of a known potent inhibitor of hepatic cytochrome P450 (CYP) 2B6, or CYP3A, activity within 1 week or within a period 5 times the drug's half-life, whichever is longer, before the first administration of study drug on Day 1.

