9.4.3 Safety Analyses

All safety analyses will be performed on the Safety Analysis Set.

Adverse Events

Adverse events will be coded using the Medical Dictionary for Regulatory Activities (MedDRA; Version 23.0 or higher). Treatment-emergent adverse events (TEAEs) are AEs with onset or worsening after the start of study treatment. The AE summaries will be primarily based on TEAEs. The number and percentage of subjects with TEAEs will be summarized by treatment group, system organ class, and preferred term for all TEAEs, treatment-related TEAEs, SAEs, serious TEAEs, severe TEAEs, TEAEs of special interest, and all TEAEs leading to study drug discontinuation. All TEAEs will be further summarized by maximum severity and causality. The TEAEs of special interest will be identified in the SAP.

All AEs will be presented in a by-subject listing. Serious AEs, severe AEs, and AEs leading to study discontinuation or death will be presented in separate listings.

Clinical Laboratory Tests

Laboratory data will be summarized using descriptive statistics for each parameter, including change from baseline at each assessment time by treatment group. Frequency tables or shift tables will be used to present the number and percentage of subjects with laboratory values within/outside reference ranges. All laboratory data will be present in the listings. A by-subject listing will also be provided for subjects with abnormal laboratory results.

Electrocardiogram

Descriptive statistics will be used to summarize the observed and change from baseline values of the following ECG parameters at each assessment time by treatment group: heart rate, PR interval, QRS interval, QT interval, and QTcF. All ECG data will be present in listings.

Vital Signs

Vital sign parameters including temperature, pulse/heart rate, respiratory rate, SpO₂, and blood pressure will be summarized descriptively for both the observed and change from baseline values at each assessment time by treatment group. Frequency tabulations will be provided for abnormalities as applicable.

Other Safety Questionnaires and Assessments

All physical examination results will be listed by subject.

Prior and concomitant therapies will be summarized separately and tabulated for each treatment group using frequencies and percentages. Percentages will be based on the number of subjects in each treatment group. Prior and concomitant medications will be listed by subject.

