Data listings will simply list the data recorded on the CRF or derived for each subject. They will be ordered by treatment, site, subject number, and time of assessment. When expedient, additional levels of ordering hierarchy may reflect subsets of assessments within subject. Data listings will not display subject initials.

Summary tables will display summary statistics calculated for each of the treatment groups, unless described otherwise in the following sections. Tables may have either of two general layouts. When the greatest interest is in direct comparison of one treatment group with the others at particular times, different columns of a summary table will display the statistics for the different treatment groups.

The summary statistics displayed will be a function of the type of data associated with the summarized assessment. Unless stated otherwise in relevant sections to follow, continuous data will be summarized with the number of non-missing values, arithmetic mean, standard deviation, minimum, quartile 1 (Q1), median, quartile 2 (Q3), and maximum. Categorical data will be summarized with the number of nonmissing values and the numbers of values equal to each of the possible values. Percentages of subjects with each of the possible values will be calculated from the number of subjects in the corresponding analysis population, unless stated otherwise. Some continuous variables may also be grouped into categorical levels and evaluated in frequency tables.

A subset or all of the following tabular column headers will be used in presenting data for the study:

- PCN-101 60 mg
- PCN-101 30 mg
- Placebo

Efficacy analysis will be implemented according to the planned randomization treatment schedule. Safety analysis will be implemented according to the actual dosed treatment.

VI. Subject Accountability

Unless otherwise indicated, the subject characteristics will be presented by treatment groups for the FAS. The same analysis will be repeated for the SAS if the composition of subjects within these analysis sets are different from the FAS.

A. Disposition

Subject disposition events (screened, randomized, completed treatment, completed the study, early discontinuation from the study along with the reason for discontinuation) will be summarized using frequency counts and percentages by treatment groups.

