For chemistry, hematology, and urinalysis, any laboratory abnormalities will be listed separately. The abnormal laboratory listing will provide the entire profile for each subject and parameter with an abnormal post-baseline result.

E. Vital Signs and Pulse Oximetry

For vital signs (systolic and diastolic blood pressure, tympanic/temporal temperature, pulse, respiratory rate) and pulse oximetry, summaries of actual values and changes from baseline will be presented by treatment group for each scheduled assessment timepoint, beginning with the Baseline visit. For this analysis, any lab collection performed on unscheduled analysis visits will not be summarized, with the exception of the inclusion of unscheduled pre-dose assessments used in the classification of baseline, as described in [Section V.B Definition of Baseline](#).

Vital signs will consist of three (3) blood pressure measurements (recorded at intervals of at least 1 minute). The arithmetic mean of the three (3) blood pressure readings will be recorded in the CRF and used for this analysis.

Temperature data collected via tympanic or temporal methods will be pooled for analysis.

The incidence of clinically relevant abnormality will be summarized by treatment. For this analysis, any unscheduled post-baseline records will be included for assessment. A listing of clinically relevant abnormality vital signs will be displayed.

Table 4 Potential Clinically Relevant Abnormalities in Vital Signs

Parameter	Unit	Low	High
Systolic blood pressure	mmHg	≤ 90 or CFB ≤ -20	≥ 180 or CFB ≥ 20
Diastolic blood pressure	mmHg	≤ 50 or CFB ≤ -15	≥ 105 or CFB ≥ 15
Pulse	beats/min	≤ 50 or CFB ≤ -15	≥ 120 or CFB ≥ 15
Temperature	°C	CFB ≤ -2	≥ 38.3 or CFB ≥ 1.1
Respiratory Rate	breaths/min	<8	Not applicable
Oxygen Saturation	%	< 90%	Not applicable

CFB = change from Baseline.

All vital signs data will be listed

F. Physical Examination

All physical examination results will be listed by subject.

G. Electrocardiograms

12-Lead ECGs will be obtained using an ECG machine that automatically calculates the parameters for analysis. If abnormal, the ECG needs to be repeated.

An overall interpretation of the ECG results, PR intervals, RR intervals, QT uncorrected intervals, QT intervals corrected by Fridericia's formula (QTcF) will be listed by subject.

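### The SAP's only laboratory shift table counts subjects normal at baseline, so worsening from an abnormal baseline has no by-arm count, and the table is narrower than Protocol 9.4.3 describes

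*SAP*

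**What the plan says.** SAP VIII.D (Clinical Laboratory Results) plans these outputs:

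- **Continuous summaries** for chemistry and hematology: "summaries of actual values and changes from baseline will be presented by treatment group for each scheduled assessment timepoint". They carry no restriction on baseline status. For them, "any lab collection performed on unscheduled analysis visits will not be summarized", except unscheduled pre-dose values that serve as baseline.
- **Shift tables** for chemistry and hematology, described only as covering patients "who were normal at baseline, but who became abnormal subsequently". Unscheduled samples are included here.
- **Listings** of all laboratory data, and a separate listing of abnormal results: "The abnormal laboratory listing will provide the entire profile for each subject and parameter with an abnormal post-baseline result".

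The shift-table sentence does not itself mention treatment group. That follows from the default in SAP V.I: "Summary tables will display summary statistics calculated for each of the treatment groups".

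Protocol 9.4.3 describes the categorical output more broadly: "Frequency tables or shift tables will be used to present the number and percentage of subjects with laboratory values within/outside reference ranges".

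Protocol 5.2, criterion 12, begins "Has moderately impaired hepatic function at screening, defined as serum alanine aminotransferase (ALT) or aspartate aminotransferase (AST" and sets the cut at more than 2 x ULN, with the same limit for total bilirubin. It applies at screening only.

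**The concern.** Safety and tolerability against placebo is a stated objective. For laboratory data, the usual way to compare arms on individual abnormal cases is a count. The SAP's count starts from normal subjects only, although the entry criteria knowingly admit subjects with raised liver tests. A subject who enters at 1.8 x ULN and rises further is not in the numerator at any level. A change from low to high is not counted either.

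The SAP is more complete in its other safety domains. Vital signs (VIII.E, Table 4) get an incidence by treatment using absolute limits, changes from baseline, or both. QTcF (VIII.G) gets counts at absolute thresholds and at increases from baseline. Neither is confined to subjects normal at baseline. The SAP gives no reason for treating laboratory data more narrowly, or for narrowing what the protocol describes.

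**Working it through.** The plan states no figure to reproduce. The check is mainly textual, with a small illustration.

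**Step 1: can subjects with an abnormal baseline be enrolled?** Yes. Criterion 12 excludes only values above 2 x ULN at screening, so values above 1 and up to 2 x ULN are admissible. Baseline is the last evaluable pre-dose value (SAP V.B), and laboratory tests are repeated on Day -1 (Protocol 1.3).

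**Step 2: where does their worsening appear?**

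| Output | Includes them? | By arm? | Limit |
|---|---|---|---|
| Shift table (SAP VIII.D) | No | Yes, by the V.I default | Normal at baseline only |
| Continuous summaries (SAP VIII.D) | Yes | Yes | Post-dose unscheduled samples omitted |
| TEAE tables (SAP VIII.B) | If recorded as an AE | Yes | Needs investigator judgement of clinical significance (Protocol Appendix 4) |
| Abnormal-value listing (SAP VIII.D) | Yes | Ordered by treatment (SAP V.I) | No numerator or denominator |

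**Step 3: can a peak value miss both by-arm laboratory tables?** Yes. Scheduled post-dose samples fall only on Days 8 and 15 (Protocol 1.3). Protocol 8.2.5 requires clinically significant abnormal values to be repeated, so some follow-up values will probably be unscheduled. In a subject abnormal at baseline, a peak at such a draw is outside the continuous summary (unscheduled) and outside the shift table (baseline status).

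**Step 4: how sensitive are the continuous summaries?** Suppose k of 31 subjects in an arm start with raised ALT and each rises by r x ULN, with all others unchanged (k and r are assumed). The arm mean change moves by k x r / 31:

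- k = 1, r = 1: 1 x 1 / 31 = 0.03 x ULN
- k = 3, r = 2: 3 x 2 / 31 = 0.19 x ULN
- k = 6, r = 3.5: 6 x 3.5 / 31 = 0.68 x ULN

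The shift table counts 0 in each case. The mean reacts little when few subjects are involved. The maximum does better: SAP V.I lists "arithmetic mean, standard deviation, minimum, quartile 1 (Q1), median, quartile 2 (Q3), and maximum", so a rise that is the arm's largest shows in full if it falls at a scheduled visit. However, samples are analysed in local laboratories with their own ranges (Protocol Appendices 2 and 3), and the SAP does not say that the summaries are scaled to each laboratory's ULN.

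**Step 5: how many subjects could be affected?** The documents give no baseline abnormality rate. Assuming 5% to 15% for a given analyte: 0.05 x 31 = 1.6 and 0.15 x 31 = 4.7, so about 2 to 5 per arm. These are subjects who cannot be counted, not subjects expected to worsen.

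**The case against.** The strongest reply is that the information is not lost. A reader might infer from the shift-table wording that worsening in these subjects is never compared between arms. The documents do not support that. The continuous summaries in the same section are by arm, cover all subjects and show quartiles and maximum. A reader might also take the shift table to be the only categorical comparison. It is not: worsening that the investigator judges clinically significant is an AE (Protocol Appendix 4), TEAEs include events that worsen after the start of infusion (SAP VIII.B), and they are tabulated by system organ class and preferred term. With a handful of subjects per analyte, a treatment-ordered listing with full profiles lets a reviewer see the cases.

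Further, Protocol 9.4.3 offers a choice of table type, and a normal-to-abnormal table does use reference ranges, so the SAP is narrower than the protocol rather than in flat contradiction with it. The SAP's silence on low versus high is not a decision to merge them, since table shells are not among the documents. Nor do the documents support describing these subjects as having the least hepatic reserve; criterion 12 reserves its label of moderate impairment for values above 2 x ULN, and criterion 5 also removes significant hepatic disease that the investigator thinks poses a risk. The trial gives a single infusion and analyses laboratory data descriptively.

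All of that stands, and it keeps the point small. What it does not supply is a by-arm count of worsening from an abnormal baseline. Each substitute has a stated limit: unscheduled samples omitted, dependence on judgement, or no count.

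**Conclusion.** The gap is real and minor. SAP VIII.D describes its one laboratory shift table more narrowly than Protocol 9.4.3 and leaves worsening from an abnormal baseline without a by-arm count, although criterion 12 admits subjects in whom this could occur. By-arm information remains through the continuous summaries and TEAE tables, so this is a weakness of presentation and not an absence of comparison. Nothing in the documents shows that a signal would be missed. The size, about 2 to 5 of 31 subjects per arm for a given analyte, rests wholly on the assumed 5-15%. The textual finding does not depend on that assumption.

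**What to change.** Replace the shift table in SAP VIII.D with a full one for each chemistry and hematology analyte and arm: baseline low, normal or high against worst post-baseline low, normal or high, with unscheduled values included as the SAP already plans for this table. State the treatment-group layout and the denominator explicitly, and say how worst is chosen when a subject has both low and high values.

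That table alone does not show a raised value rising further, because high-to-higher stays in one cell. So for ALT, AST and bilirubin add a by-arm table of multiple-of-ULN category at baseline against the worst post-baseline category, using the local ranges already collected. Fix the category limits before unblinding.

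The cost is a change to table shells and some programming on data already collected. SAP I.B allows modification until database lock. The change brings the SAP into line with Protocol 9.4.3, so the protocol need not be amended.
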